3.3 Enrollment Procedures

To enter a patient, the investigator or study team will contact the CRS representative. All eligibility requirements must be reviewed prior to the patient entering the study. The following information must be provided to the CRS representative:

- 1) Completed and signed eligibility checklist.
- 2) All pages of the original signed informed consent forms (ICFs), including HIPAA form B.
- 3) Relevant source documents such as: subject medical history and physical exam; admission or discharge notes; diagnostic reports; pathologic confirmation of diagnosis by University of Miami pathologists (UM review) and relevant subject-specific communication.
- 4) To assure compliance with early stopping for toxicity, the monitor will inform the study team when the forth patient may be enrolled.

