3.3.1 Cancellation Guidelines

If a patient does not receive protocol therapy, the patient may withdraw. Patients who are enrolled on study but not treated with the LEAD component of the protocol will be excluded from all analyses.

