9.1 Definitions

- *Feasibility*: The proportion of enrolled patients for whom LEAD RT dose can be successfully administered following MRI-guided planning.
- *Acute toxicity*: Grade 2 or higher treatment-related acute GU/GI toxicity occurring during treatment and within 30 days of completing treatment. The severity of the reactions to the treatment is scored according to the criteria outlined in Appendix II.
- *Late toxicity*: Delayed toxicities are usually related to urinary, rectal, and sexual function. The anticipated urinary and rectal toxicities and severity criteria are shown in Appendix II.
- *Biopsy failure rate*: The proportion of positive biopsy findings among patients without clinical or biochemical failure 2-2.5 years after completing study treatment.
- *Biochemical failure-free interval (BFFI)*: The elapsed time from study enrollment to first documented evidence of biochemical failure ($PSA \geq \text{nadir}+2$). In the absence of biochemical failure, follow-up time will be censored at the date of last documented biochemical failure-free status.
- *Biochemical failure (BF) rate*: The cumulative incidence of BF allowing for competing risk as needed.
- *Biochemical failure-free survival (BFFS)*: The elapsed time from study enrollment to first documented evidence of biochemical failure or death from any cause, whichever occurs first. In the absence of any event defining biochemical failure, follow-up time will be censored at the date of last documented biochemical failure-free status.
- *Failure-free interval (FFI)*: The elapsed time from study enrollment to first documented evidence of biochemical or clinical failure. Clinical failure is defined as local failure due to newly identified extension outside of the prostate after initial regression, or urinary obstructive symptoms with carcinoma found at TURP or regional/distant failure due to radiographic evidence metastasis (nodal or hematogenous spread). In the absence of any event defining failure, follow-up time will be censored at the date of last documented failure-free status.
- *Failure rate*: The cumulative incidence of biochemical or clinical failure allowing for competing risk as needed.

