14.4 Interim Monitoring

We propose the following guidelines for the Sylvester Data and Safety monitoring Committee (DSMC) (see also Appendix III) in its review of accumulating data on toxicity and feasibility of study treatment. The proposed guidelines were developed using Bayesian methods, which can be applied at any stage of enrollment without advance specification of the number of interim analyses to be performed, or the number of patients evaluable for toxicity, or response, at the time such assessments are made.^{95,96}

Under the Bayesian method, we assign a prior probability (level of belief at the start of the trial) to a range of possible values for the true toxicity rate, and likewise for the true feasibility rate. As data on treated patients become available, each of these probability

Number of Patients With acute treatment Related Grade 3+ GI/GU Toxicity	Total Patients Evaluated	Observed Rate
2	3 to 6	≥33% (2 of 6)
3	7 of 11	≥27% (3 of 11)
4	12 to 16	≥25% (4 of 16)
7	17 to 25	≥25% (7 of 25)

distributions is revised and the resulting posterior probability becomes the basis for recommending either early termination or continuation of the study. In the sections that follow, we provide specific stopping guidelines based on posterior probabilities for monitoring toxicity and efficacy over the course of this trial. Underlying assumptions for the prior distributions are also presented.

Stopping rules for safety: The following early stopping guidelines, which are based on a Bayesian method, will be

applied to ensure safety of this Phase I trial. Safety monitoring will be based on the occurrence of treatment related (possible, probable, or definite) grade 3 or higher GI or GU toxicity occurring during study treatment or within 30 days of treatment completion. Early stopping (suspension and possibly termination) will be considered if there is evidence that the proportion of patients experiencing such toxicity exceeds 15%. Specifically, we suggest as a guideline for early termination a posterior probability of 80% or higher that the rate of grade 3 or higher GI/GU toxicity exceeds 15%. **Table 2** shows specific instances where this guideline is met, thus suggesting early termination due to evidence of excessive toxicity.

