As an additional safeguard, the first three patients enrolled on study will be observed for 30 days following treatment completion of the third patient before enrollment is continued (fourth patient). If two or three of the first three study patients have grade 3 or higher GI/GU toxicity within 30 days of treatment completion, enrollment will be suspended pending DSMC review. If none or one of the first three patients enrolled on study have grade 3 or higher GI/GU toxicity

within 30 days of treatment completion, enrollment will continue without restriction on the interval between successive enrollments.

Posterior probabilities used to derive the preceding table are calculated under a prior beta distribution with parameters $\beta_1 = 0.2$ and $\beta_2 = 1.8$, which corresponds to an expected rate of 15% based on prior information roughly equivalent to having studied 2 patients^{96,97}. Furthermore, this prior distribution assigns a small a priori chance (32%) to the possibility that the true rate of unacceptable toxicity is 15% or greater.

Table 3. Stopping Rules For Lack of Feasibility

Number of Patients ineligible For LEAD	Total Patients enrolled and completed CT simulation	Observed LEAD ineligibility rate
2	3	67%
3	4 to 6	≥50% (3 of 6)
4	7 to 10	≥40% (4 of 10)
5	11 to 13	≥38% (5 of 13)
6	14 to 17	≥35% (6 of 17)
9	18 to 25	≥35% (9 of 25)

Stopping rules for lack of feasibility

Similarly, for purposes of monitoring the feasibility of delivering LEAD RT, we consider the proportion of patients enrolled on study for whom it is not possible to deliver LEAD RT as determined from CT/MRI simulation and planning, referred to as the *LEAD ineligibility rate*. The LEAD treatment will not be delivered if the summed dose of LEAD and conventional treatment to critical structures exceeds tolerance. Early stopping due to infeasibility of the proposed study treatment will be considered if there is evidence that the rate of LEAD ineligibility exceeds

20%. Specifically, we suggest as a guideline for early termination a posterior probability of 90% or higher that the rate of unacceptable toxicity exceeds 20%. **Table 3** shows specific instances where this guideline is met, thus suggesting early termination due to early evidence of LEAD infeasibility.

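### The safety lead-in counts the first three patients enrolled, not the first three given LEAD RT, so its wording permits release of enrolment on two LEAD exposures

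*Combined protocol and SAP*

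**What the plan says.** **The hold.** Section 14.4 (Interim Monitoring) adds a safeguard to the Bayesian guidelines: "the first three patients enrolled on study will be observed for 30 days following treatment completion of the third patient before enrollment is continued". Suspension pending review by the Data and Safety Monitoring Committee (DSMC) is worded "If two or three of the first three study patients have grade 3 or higher GI/GU toxicity" within 30 days of completing treatment. Release is worded "If none or one of the first three patients enrolled on study have grade 3 or higher GI/GU toxicity" in that period; enrolment then continues with no restriction on spacing. Section 3.3 item 4 also works by patient number: "the monitor will inform the study team when the forth patient may be enrolled".

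**LEAD eligibility comes later.** Fiducial placement follows enrolment (4.3), and the simulation MRI comes at least one week after that (4.6). Section 14.4 then says: "The LEAD treatment will not be delivered if the summed dose of LEAD and conventional treatment to critical structures exceeds tolerance". Feasibility in 9.1 is accordingly "The proportion of enrolled patients for whom LEAD RT dose can be successfully administered following MRI-guided planning". Enrolled patients who never receive LEAD RT are therefore foreseen.

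**What is said about such patients.** Section 3.3.1: "Patients who are enrolled on study but not treated with the LEAD component of the protocol will be excluded from all analyses". Section 14.4 describes the Bayesian updating with the words "As data on treated patients become available". No section says that a LEAD-ineligible patient is replaced in the lead-in, or that the hold is extended. Section 14.5 (Reporting and Exclusions) is marked N/A.

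**The concern.** The lead-in is the only step that restricts the pace of entry before enrolment opens fully. Its purpose is to see the acute toxicity of the LEAD fraction plus IMRT in three men first. A patient found LEAD-ineligible at planning tells us nothing about that toxicity, yet takes one of the three places under the wording used.

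If exactly one of the first three is ineligible, the rule of two or more events operates on two exposed men. Unless the unexposed man has a countable event, suspension needs toxicity in both of them. Those at stake are the patients enrolled while the third LEAD-exposed patient is still under treatment or observation. Under a lead-in of three exposed patients they would have waited.

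**Working it through.** **Inputs from the plan**
- Feasibility prior Beta(0.4, 1.6), mean 20%. Stop if P(ineligibility rate > 20%) is at least 0.90 (14.4, Table 3).
- Toxicity prior printed as Beta(0.2, 1.8). Stop if P(grade 3+ rate > 15%) is at least 0.80 (14.4, Table 2).
- Lead-in suspends at 2 or 3 events among three patients (14.4).
- 38 fractions over 7.5 weeks (4.15); 25 patients over two years (14.1).

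**Assumptions.** Patients are independent, accrual is uniform, and the patient not given LEAD has no countable event (relaxed in step 4). The ineligibility rate q is shown at 10% (the prior median is 10.4%), at 20% (prior mean, and also the infeasibility threshold), and averaged over the prior. The plan gives no toxicity rate for LEAD, so t = 15%, 30% and 40% are used.

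**Step 1. Does Table 3 catch the case?** The posterior after x ineligible of n is Beta(0.4 + x, 1.6 + n − x).
- Prior P(rate > 20%) = 0.361, which reproduces the plan's 36%.
- 2 of 3: Beta(2.4, 2.6) gives 0.907, at or above 0.90, which reproduces the first row of Table 3.
- 1 of 3: Beta(1.4, 3.6) gives 0.601, below 0.90. The rule is not met.

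So one ineligible patient of three passes. Two or three do not, and are left out of the claim.

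**Step 2. Does the toxicity criterion catch one event in two exposed patients?** The printed Beta(0.2, 1.8) has mean 10% and P(rate > 15%) = 21.6%, not the stated 15% and 32%. It gives 0.775 at 2 of 6 and 0.781 at 3 of 11, below 0.80 although Table 2 lists both. Beta(0.3, 1.7) gives a mean of 15%, a tail of 32.3%, and 0.801 at both points. Both priors are therefore shown.

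| Events / exposed | Beta(0.2, 1.8) | Beta(0.3, 1.7) |
|---|---|---|
| 1 of 2 | 0.714 | 0.757 |
| 1 of 3 | 0.623 | 0.669 |
| 2 of 3 | 0.925 | 0.939 |

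One of two is below 0.80 under either prior.

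**Step 3. How often?** Exactly one of three ineligible has probability 3q(1 − q)². Two thirds of this is patient 1 or 2, and one third is patient 3.

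| | Prior-averaged | q = 10% | q = 20% |
|---|---|---|---|
| Exactly one of three | 20.8% | 24.3% | 38.4% |
| Patient 1 or 2 | 13.9% | 16.2% | 25.6% |
| Patient 3 | 6.9% | 8.1% | 12.8% |

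**Step 4. Chance of suspension.** With three exposed it is 3t²(1 − t) + t³. With two exposed it is t².

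| True rate t | Three exposed | Two exposed | Difference |
|---|---|---|---|
| 15% | 6.1% | 2.3% | 3.8 points |
| 30% | 21.6% | 9.0% | 12.6 points |
| 40% | 35.2% | 16.0% | 19.2 points |

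If the patient not given LEAD has a countable event with probability s, the two-exposed figure is t² + 2t(1 − t)s. For s from 0 to 5% this is 9.0% to 11.1% at t = 30%, and 16.0% to 18.4% at t = 40%.

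**Step 5. Averaged loss.** Among cases Table 3 does not flag, the weight of the one-ineligible case at q = 10% is 0.243 / 0.972 = 0.25 (prior-averaged: 0.208 / 0.832 = 0.25). The loss is 0.25 × (3.8, 12.6, 19.2) = 1.0, 3.2 and 4.8 points. Leaving out the cases where patient 3 is the ineligible one, the weight is 0.162 / 0.891 = 0.182 and the loss is 0.7, 2.3 and 3.5 points.

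**Step 6. Who is affected?** One LEAD patient's window is 1 + 52.5 + 30 = 83.5 days. At 25 patients in 730 days, 83.5 × 25 / 730 = 2.9, so about 3 patients enrol within it.

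**The case against.** **LEAD-treated patients were plainly meant.** The lead-in speaks of completing treatment, the monitoring text of data on treated patients, and 3.3.1 removes patients not given LEAD from analyses. This is a fair reading of intent, and I do not suggest that the sponsor meant to release on two exposures. But 3.3.1 governs analyses, not the enrolment hold, and supplies no replacement. The hold, the suspension rule, the release rule and 3.3 item 4 all run on enrolment or patient number.

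**Completing treatment is undefined for any patient not given LEAD.** This stands. It is plainest when patient 3 is the ineligible one, because the clock is tied to that patient, and release should not be inferred there. It also applies to the toxicity status of an ineligible patient 1 or 2. The wording permits release in those cases, but how it would be applied is uncertain.

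**Other safeguards exist.** Toxicity is reviewed weekly during treatment (5.2), the guidelines apply at any stage of enrolment, a monitor must clear the fourth patient (3.3), and the DSMC can suspend the study (Appendix III). A second event, in the third LEAD patient, would meet Table 2 at once. Section 10.0 calls grade 3 or 4 acute toxicity rare, and 4.8 reports favourable preliminary dosimetry, so the lower ineligibility figures may be nearer. All of this limits the harm. None of it restores the third exposure before entry opens.

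**A stronger reading that does not hold.** A reader might infer that the third LEAD patient loses protection. The documents do not support this: 14.4 does not stagger entry among the first three, so that patient could be treated before the others finish observation under any version of the rule. The loss falls on later enrollees.

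**Conclusion.** The point holds as a gap in wording, and it is minor. The stated rule permits enrolment to be released on two LEAD exposures when exactly one of the first three patients is ineligible, and neither stopping table prevents it at one event in two. The conclusion is the same under both candidate toxicity priors.

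In the affected cases the chance of suspension is less than half of what three exposures would give, for any true rate below 50% (the ratio is 1/(3 − 2t)). Averaged over the cases Table 3 leaves open, the loss is small. An intact three-patient lead-in is itself a weak screen: it suspends only 6.1% of the time at the 15% threshold, and the plan already accepts one event in three. The larger losses need toxicity rates well above what the protocol expects.

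The figures rest on independence between patients, uniform accrual, the ineligibility rates shown, and no countable event in the patient not given LEAD. It should not be read as a claim that release will happen, or that it could follow with fewer than two exposures and no flag: two or three ineligible of three already meet Table 3.

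**What to change.** In 14.4:
- Define the hold, the suspension rule and the release rule by the first three patients treated with LEAD RT.
- Start the 30 days when the last of these three completes or permanently stops protocol radiotherapy, so that the clock is defined in every case.
- State that an enrolled patient not given LEAD RT does not count toward the three and is replaced, and that during the hold enrolment is open only for such a replacement.

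Reconcile 3.3 item 4, so that the monitor's clearance depends on three LEAD-treated patients and not on the fourth enrolment number. Reconcile 3.3.1, so that it says how patients not given LEAD are handled in the lead-in.

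The change is to wording only. When a replacement is needed, the hold may lengthen by recruitment, planning and treatment time; the documents do not allow that time to be fixed. Expected enrolments to reach three exposed patients are 3/(1 − q): 3.33 at 10% ineligibility and 3.75 at 20%, instead of 3.

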4.15 Duration of Therapy

- Within 4 weeks of enrollment, patients will be biopsied (patient may refuse) and fiducial markers placed.
- LHRH agonist androgen deprivation therapy: LHRH agonist therapy may start up to two months prior to signing consent form or any time after signing consent form, up to two weeks after fiducial marker placement (preferred) in men with intermediate or high (optional) risk prostate cancer. All patients may receive 4-6 months (+/- 2 months) LHRH agonist therapy.
- Anti-androgen treatment should begin 1-14 days prior to LHRH agonist injections. Anti-androgen will be continued four 4 months.
- .
- Standard fraction RT: Day 2 of radiotherapy will start within 32 hr of LEAD RT and will consist of 38 fractions at 2.0 Gy over 7.5 weeks
- Treatment will be stopped for grade 4 acute toxicity (according to the current version of Common Terminology Criteria for Adverse Events (CTCAE version 4), but may be resumed per protocol if the treatment break is less than 10 working days. Since we have never observed grade 4 toxicity acutely using IMRT (conformal CyberKnife treatment is an IMRT-like treatment),

such an event is unlikely. If grade 4 toxicity resolves beyond the 10 days the treating physician will decide whether to give additional RT.

- Treatment will be stopped if metastasis is detected by radiographic or pathologic evidence and the patient will be removed from the study, but not from intent-to-treat analysis. A work-up for metastasis during treatment will only be carried out if the treating physician deems necessary.
- Multiparametric MRI exams of the prostate/pelvis will be carried out after RT at 3 months, 9 months, and within 2 months of the post-treatment prostate biopsies.
- Prostate biopsies will be taken at 2-2.5 years post completion of all therapy.

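### Section 14.4 has no enrolment trigger for severity above grade 3: one grade 4 or fatal GI/GU event in the first three patients is handled as one grade 3 event

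*Combined protocol and SAP*

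**What the plan says.** Section 14.4 bases safety monitoring on "treatment related (possible, probable, or definite) grade 3 or higher GI or GU toxicity" and gives the window for counting these events as "occurring during study treatment or within 30 days of treatment completion". It suggests early termination at "a posterior probability of 80% or higher that the rate of grade 3 or higher GI/GU toxicity exceeds 15" per cent. Table 2 lists the counts that meet this: 2 among 3 to 6 patients evaluated, 3 among 7 to 11, 4 among 12 to 16, and 7 among 17 to 25.

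The additional safeguard covers the first three patients. "If two or three of the first three study patients have grade 3 or higher GI/GU toxicity within 30 days of treatment completion", then "enrollment will be suspended pending DSMC review". The other branch covers lower counts: "If none or one of the first three patients enrolled on study have grade 3 or higher GI/GU toxicity" in the same 30-day window, then "enrollment will continue without restriction on the interval between successive enrollments".

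On how unusual a severe acute event would be, Section 4.15 says: "Since we have never observed grade 4 toxicity acutely using IMRT". Section 10.0 describes acute toxicity of grade 3 or 4 as rare in the investigators' experience.

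**The concern.** Grades 3, 4 and 5 each add one to the count, so neither the lead-in nor Table 2 can react to severity. One grade 4 or fatal GI/GU event among the first three patients meets the condition under which the text says enrolment goes on. The only thing lifted at that point is the wait between patients, but the stated action is still to continue. A treatment-related death from another cause, or after the window closes, adds nothing to the count.

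Toxicity is part of the primary objective (Section 2.1), the technique is presented as novel (Section 1.2), and the protocol reports no acute grade 4 event with IMRT. On that background a single grade 4 or 5 event would be informative, and the written rule gives it no special weight. At stake is whether further patients are treated before anyone is obliged to review such an event.

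**Working it through.** **Inputs (all Section 14.4).** Toxicity threshold 15%; posterior cut-off 80%; printed prior Beta(0.2, 1.8); stated prior mean 15% and stated prior chance of 32% that the rate is 15% or more. The printed parameters give a mean of 0.2/2.0 = 10% and a chance of 21.6%. Beta(0.3, 1.7) gives 15% and 32.3%, matching the stated figures, so both priors are carried through.

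**Formula.** With x events in n patients the posterior is Beta(a + x, b + n − x), and the quantity compared with 0.80 is P(rate > 0.15).

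**The plan's own boundary first, then single events.**

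| Events / patients | Beta(0.2, 1.8) | Beta(0.3, 1.7) | 80% met? |
|---|---|---|---|
| 2 of 3 | 0.925 | 0.939 | yes |
| 1 of 3 | 0.623 | 0.669 | no |
| 1 of 2 | 0.714 | 0.757 | no |
| 1 of 1 | 0.813 | 0.849 | yes |

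The lead-in boundary is reproduced under either prior: 2 of 3 suspends, 1 of 3 continues. Grade does not enter the formula, so 0.623 or 0.669 applies whether the one event is grade 3, 4 or 5.

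**How far the printed rows tolerate severe events.** Every row of Table 2 needs at least 2 events. Counts that meet no printed row are 1 by patient 6, 2 by patient 11, 3 by patient 16 (3/16 = 19%; 3/12 = 25%) and 6 by patient 25 (6/25 = 24%), even if all are grade 4 or 5. At 6 of 25 the posterior is 0.840 or 0.852, so the 80% criterion is met there although the printed row asks for 7. That mismatch in the last row is a separate matter and does not affect the 1-of-3 result.

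**Other provisions, set beside the gap.**

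- Sections 4.15 and 12.0 stop the affected patient's treatment at acute grade 4. They say nothing about enrolment.
- Section 11.3.6 requires unanticipated deaths to reach the IRB within 24 hours. No enrolment hold is attached.
- Section 3.3 has the monitor release the fourth patient, to ensure that the toxicity stopping rule is followed. That rule continues at 0 or 1.
- Appendix III gives the DSMC continuing review of adverse events and general power to suspend or terminate, with no event-specific trigger. For assessing adverse events it points to Section 11.0, not 14.4.

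**Cost of a single-event hold.** The documents give no grade 4-5 rate, so q is an assumed per-patient rate with independent patients.

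| q | Hold in first 3: 1 − (1 − q)³ | Current 2-of-3 rule if these are the only counted events: 3q²(1 − q) + q³ | At least one event in 25: 1 − (1 − q)²⁵ |
|---|---|---|---|
| 1% | 3.0% | 0.03% | 22% |
| 2% | 5.9% | 0.12% | 40% |
| 5% | 14.3% | 0.73% | 72% |

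The last column slightly overstates the chance of an accrual pause, since an event after the last enrolment delays nobody.

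**The case against.** Section 14.4 offers guidelines to a committee, not an automatic rule. Its language on stopping is advisory, and nothing confines the DSMC to the listed counts. The DSMC reviews adverse events as they accrue and can suspend at any time, deaths go to the IRB within a day, and Appendix IV calls for weekly data submission in phase I. The trial is also subject to the cancer center's DSM Plan, which is linked but not reproduced and may already require a hold. Pooling grade 3 and above is a stated design choice, with nothing miscalculated.

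Most of this stands, and it rules out several stronger readings.

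- A reader might infer that enrolment becomes unrestricted. It does not: only the interval between patients is freed, and the Bayesian guideline and DSMC review remain in force.
- A reader might infer that the team is told to ignore a death, or that the trial has no safeguard against one. The documents do not say so; they leave the matter to discretion.
- A reader might infer that the Bayesian guideline can never act on one event. Section 14.4 allows it to be applied at any stage, and 1 event in 1 patient gives 0.813 or 0.849, above 80%. The printed rows start at three patients, and grade plays no part in either case.
- A reader might infer that every treatment-related death counts as one grade 3 event. Only a GI/GU death inside the window does; any other counts as zero.

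What the objection does not remove is the wording of the lead-in, which states continuation as the action at none or one. A safety rule should not depend on the committee overriding it in the most serious case.

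**Conclusion.** The concern holds in a limited form. Within Section 14.4 nothing above grade 3 changes the enrolment decision: one related grade 4 or fatal GI/GU event among the first three patients leads to continued enrolment, no printed row of Table 2 acts on a single event, and related deaths outside the GI/GU category or the window are not counted. Any suspension then rests on DSMC discretion or on a DSM Plan that cannot be checked here. The 1-of-3 result is the same under the printed prior and under the prior that matches the stated mean.

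The documents support saying that 14.4 lacks a severity trigger. They do not support saying that the trial as governed lacks one, nor that this is a flaw that must be corrected before the trial can proceed. It is a recommended, inexpensive improvement. The pause probabilities rest on assumed rates; the protocol's report of no acute grade 4 toxicity with IMRT points to the low end, but that experience is not with the LEAD fraction.

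**What to change.** Add one sentence to the lead-in paragraph and beneath Table 2:

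> Irrespective of the counts above, any grade 5 event, or any grade 4 GI/GU event, possibly, probably or definitely related to study treatment suspends enrolment pending DSMC review.

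This is a trial-level hold for review, not termination. It leaves the patient-level treatment rules in Sections 4.15 and 12.0 as they are, and it leaves the count-based boundaries unchanged.

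The cost is one amendment sentence and, when triggered, a short accrual pause. Such a pause should not be described as certain to be rare: the chance of at least one over 25 patients is about 22% at an assumed rate of 1%, 40% at 2% and 72% at 5%. If the DSM Plan already contains an equivalent hold, a cross-reference to it in Section 14.4 would be enough.

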Posterior probabilities used to derive the preceding table are calculated under a prior beta distribution with parameters $\beta_1 = 0.4$ and $\beta_2 = 1.6$, which corresponds to an expected rate of 20% based on prior information roughly equivalent to having studied 2 patients. Furthermore, this prior distribution assigns a small a priori chance (36%) to the possibility that the true rate of unacceptable toxicity is 20% or greater.

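### The printed safety prior, Beta(0.2, 1.8), contradicts its own stated mean (15%) and tail (32%), and under it Table 2 misses the 80% guideline at n = 6, 11 and 16

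*Combined protocol and SAP*

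**What the plan says.** Section 14.4 (Interim Monitoring) gives the monitoring committee a Bayesian guideline for treatment-related grade 3 or higher acute GI/GU toxicity. The trigger for considering a stop is "a posterior probability of 80% or higher that the rate of grade 3 or higher GI/GU toxicity exceeds 15" per cent. Table 2 "shows specific instances where this guideline is met, thus suggesting early termination due to evidence of excessive toxicity". Its rows are 2 events at n = 3 to 6, 3 at n = 7 to 11, 4 at n = 12 to 16, and 7 at n = 17 to 25.

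The section says the posteriors behind the table rest on a Beta(0.2, 1.8) prior. It summarises the centre and weight of that prior in these words: "which corresponds to an expected rate of 15% based on prior information roughly equivalent to having studied 2 patients". It adds that "this prior distribution assigns a small a priori chance (32%) to the possibility that the true rate of unacceptable toxicity is 15% or greater".

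The feasibility rule later in the section is built the same way. Its prior is Beta(0.4, 1.6), "which corresponds to an expected rate of 20% based on prior information roughly equivalent to having studied 2 patients", with a stated 36% chance that the rate is 20% or more.

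**The concern.** The mean of a Beta(a, b) distribution is a/(a + b). With 0.2 and 1.8 that is 10%, so the stated 15% cannot belong to the printed parameters. This matters beyond a misprint because the section names this prior as the source of Table 2 and says the method can be applied at any stage of enrolment. Someone preparing a committee report may therefore recompute the posterior from the printed parameters. If parameters, mean, tail and table disagree, the committee has more than one version of the safety rule, and the version used could decide whether a given count triggers review. Toxicity is part of the primary objective (section 2.1).

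**Working it through.** **Inputs (all from section 14.4).** Printed prior Beta(0.2, 1.8); stated mean 15%; stated weight about 2 patients (a + b = 2); stated P(rate ≥ 15%) = 32%; guideline: posterior P(rate > 15%) ≥ 80%; the four rows of Table 2.

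**Formulas.** Prior mean = a/(a + b). Prior tail = P(Beta(a, b) > 0.15). After x events in n patients, posterior = P(Beta(a + x, b + n − x) > 0.15).

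**Step 1: the plan's own summary of the prior.**

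| Prior | Mean | P(rate > 15%) |
|---|---|---|
| Stated in the plan | 15% | 32% |
| Beta(0.2, 1.8), as printed | 0.2/2.0 = 10% | 21.6% |
| Beta(0.3, 1.7) | 0.3/2.0 = 15% | 32.3% |

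The printed parameters reproduce neither figure. A mean of 15% with a + b = 2 requires a = 0.3 and b = 1.7, and that prior also gives the stated tail.

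As a check on convention, the feasibility prior Beta(0.4, 1.6) gives mean 0.4/2.0 = 20% and P(rate > 20%) = 36.1%. Both match what is stated for it, so the mismatch in mean and tail is confined to the safety prior.

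**Step 2: the upper end of rows 1 to 3, against 80%.**

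| Events/n | Beta(0.2, 1.8) | Beta(0.3, 1.7) |
|---|---|---|
| 2/6 | 77.5% | 80.1% |
| 3/11 | 78.1% | 80.1% |
| 4/16 | 79.2% | 80.9% |

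Under the printed prior the shortfalls are 2.5, 1.9 and 0.8 points. Rows 1 to 3 cover 14 sample sizes (4 + 5 + 5). The printed prior disagrees with the table at these three and agrees at the other 11.

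**Step 3: smallest count that reaches 80%.**

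| Events | Beta(0.2, 1.8) | Beta(0.3, 1.7) | Table 2 |
|---|---|---|---|
| 2 | n = 3–5 | n = 3–6 | n = 3–6 |
| 3 | 6–10 | 7–11 | 7–11 |
| 4 | 11–15 | 12–16 | 12–16 |
| 5 | 16–21 | 17–21 | not listed |
| 6 | 22–25 | 22–25 | not listed |
| 7 | – | – | 17–25 |

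Beta(0.3, 1.7) reproduces rows 1 to 3 exactly. Neither prior reproduces row 4.

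**Step 4: row 4.** Posteriors, Beta(0.2, 1.8) then Beta(0.3, 1.7): 5/17 = 90.1%, 91.0%; 5/21 = 80.5%, 81.9%; 6/22 = 90.0%, 90.9%; 6/25 = 84.0%, 85.2%. All meet the guideline, yet the table shows no signal until 7 events, where 7/25 is already at 93.0% and 93.6%.

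**Step 5: effect on the chance of stopping.** Exact binomial path calculation, assuming a check after every patient from n = 3 to n = 25:

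| True rate | 80% rule, Beta(0.2, 1.8) | 80% rule, Beta(0.3, 1.7) | Table 2 as printed |
|---|---|---|---|
| 15% | 34.5% | 38.3% | 34.9% |
| 20% | 57.1% | 60.5% | 55.0% |
| 25% | 76.2% | 78.4% | 72.7% |

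The first two columns differ only through the prior: 60.5 − 57.1 = 3.4 points at a true 20% and 78.4 − 76.2 = 2.2 points at 25%. The last two differ only through row 4: 60.5 − 55.0 = 5.5 points at 20% and 78.4 − 72.7 = 5.7 points at 25%.

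**The case against.** The best defence is that two digits are misprinted and nothing else is wrong with rows 1 to 3. If Beta(0.3, 1.7) was used, those rows are correct and the shortfalls at n = 6, 11 and 16 never arise in practice. Even under the printed prior they are at most 2.5 points. The rule is advisory, the committee is handed explicit counts, and the pause after the first three patients is also written as counts (2 of 3 gives 92.5% or 93.9%, above 80% either way).

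This is fair on size, and the shortfalls should be read as conditional on the printed prior. It does not remove the contradiction: the documents cannot show which prior was used, and the section says the table was derived from the printed one.

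On row 4, the plan claims only that the table shows instances where the guideline is met, and 7 events at n = 17 to 25 do meet it. That also stands: the row is not false. But rows 1 to 3 are minimum boundaries under Beta(0.3, 1.7), and row 4 departs from that pattern without explanation, so a committee using the table would see no signal at 5/17 although the posterior is at least 90%.

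Two further limits apply. A look after every patient is an assumption; section 14.4 sets no schedule, and toxicity counts up to 30 days after treatment, so outcomes lag enrolment. And Table 3 has a marginal miss of its own: 4 of 10 gives 89.5% under Beta(0.4, 1.6), against its 90% guideline. A near miss in a table is therefore not proof of a wrong prior; the diagnosis rests on the mean and tail as well.

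**Conclusion.** The concern holds. The printed parameters, the stated mean, the stated tail and Table 2 cannot all be true. The mean is 10% rather than 15% and the tail 21.6% rather than 32%. These two results follow from the printed parameters alone, without further assumptions.

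That the parameters are the misprint is an inference, though a strong one, since Beta(0.3, 1.7) recovers the mean, the tail, the weight and three table rows together. Recomputing from the printed prior changes the advice in both directions: one more event needed at n = 6, 11 and 16, and one or two fewer at n = 17 to 25.

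Row 4 is a separate discrepancy that correcting the prior does not cure. Under a look after every patient, it costs 5 to 6 points of stopping probability at true rates of 20% to 25%. Because this is the trial's safety threshold, it must be fixed.

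**What to change.** The sponsor should confirm which prior generated Table 2.

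- **If Beta(0.3, 1.7):** correct the two printed parameters. Rows 1 to 3 stand.
- **If Beta(0.2, 1.8):** restate the mean as 10% and the tail as 22%, and recompute the whole table against the 80% guideline: 2 events at n = 3–5, 3 at 6–10, 4 at 11–15, 5 at 16–21, 6 at 22–25.
- **In either case:** reconcile row 4 with the 80% guideline, or state the different threshold it applies and why.

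The cost is two numbers and one table row in the first case, and two stated figures and Table 2 in the second. No new data or procedures are needed.
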